### 3.2 Study Schedule

**Figure 1:** Study Design or Schema for 12 Months of Follow Up

**Figure 2: Study Design or Schema for 6 Months of Follow Up**

### **3.3 Study Timeline**

Study to complete target enrollment in 18 months of recruitment. Participants will be followed for 6 and/or 12 months after initiating PrEP.

### **3.4 Study Locations**

Study procedures and data collection will take place in the metropolitan areas of Atlanta, GA, Boston MA, Jackson, MS, St. Louis, MO, and Cleveland, OH. The sites where the study will be conducted include PRISM Health Research Center (Atlanta), The Fenway Institute (Boston), UMMC with clinic space at Open Arms Health Care Center and Express Personal Health (Jackson), The Infectious Disease Clinic at Washington University (St. Louis), and MetroHealth (Cleveland). Each site will have a study clinician prescribing PrEP to site patients and site staff to support study conduct. Study participants will be completing the PrEP support kits in their homes or another private location of their selection.

### **3.5 Study Population**

#### **3.5.1 Sample**

The study population includes born males, ages 18 to 49 years, who have sex with men. Eligible men will be residents of metropolitan areas of Atlanta, Georgia; Boston, Massachusetts; Jackson, Mississippi; St. Louis, Missouri, or Cleveland, Ohio. Total sample size will be 396, with 50% minority and 50% age 18-34.

#### **3.5.2 Participant Eligibility**

After recruitment, we will use a three-stage process to screen participants for eligibility. For Stage 1, a screener will be used to determine study visit eligibility. The screener will be conducted in Alchemer, self-completed by all participants excepting those that require a phone call, in which case the screener form will be filled by study staff. The initial eligibility criteria include (1) male at birth, (2) age 18-49, (3) live in the metro area of a study site, (4) self-report HIV negative status, (5) own a smartphone, (6) not currently taking PrEP or <3 months of PrEP use in lifetime or stopped taking PrEP >6 months ago, (7) not enrolled in an HIV prevention trial, (8) willing to use study-provided PrEP navigation services to obtain PrEP, and (9) willing to use a home test kit. Those eligible for a visit based on the screener results will be shown the full study consent to review and sign. Consented participants will be called to confirm consent and for further eligibility determination. This step may take up to two weeks.

Stage 2 of eligibility assessment will be participant visit with study staff, either conducted in clinic or via telehealth consultation over Zoom. Decision will be made depending on clinic ability to conduct in-person visits and participant preference. Participants will complete a more detailed behavioral screening (based on CDC and WHO guidelines for PrEP initiation) and screened for clinical eligibility for PrEP and other study eligibility criteria: (1) report anal sex with a man in the past 6 months, (2) provide at least 2 means of alternate contact, (3) willing to take a photo of PrEP prescription label, (4) ability to complete English-language forms, (5) willing to take and adhere to PrEP daily dosing, (6) willing to obtain PrEP for a year, even if financial assistance is not available, (7) HIV-negative rapid and laboratory test or 4th gen HIV test only, (8) no symptom(s) that could indicate acute HIV infection, (9) creatinine clearance  $\geq 60$  ml/min, (10) no contraindications to taking Tenofovir Disoproxil Fumarate/ Emtricitabine (TDF/FTC) or Tenofovir Alafenamide/ Emtricitabine (TAF/FTC), (11) no history of hemophilia and (12) successful completion of a selffinger prick at study site or home. Participants will be called by the study staff with lab results. Participants who are Stage 2 eligible for the study will be provided a prescription by the site study clinician. PrEP prescription can be called in or given to participant while waiting for 4th gen HIV

and creatinine clearance results as long as rapid HIV test is documented negative and participant meets other eligibility criteria. Participants who are ineligible will be linked to care as needed. If more than four weeks pass since initial visit, then participants will need to rescreen for PrEP eligibility, including a repeat HIV test. Participants may be able to rescreen if symptoms of acute HIV infection are no longer present and HIV infection is ruled out per local protocol.

Stage 3 screening will be verification that HIV 4th generation and creatinine clearance tests indicate eligibility and a PrEP prescription has been filled. Using our electronic software (described below) the survey will prompt participants to use their smartphone to take a photo of their prescription label that identifies their name, date of prescription, and the medication name. We anticipate this to occur within one week of receiving the prescription. Once this brief process is completed, participants will be enrolled into the trial.

### **3.5.3 Inclusion Criteria**

- Male at birth
- Age 18-49
- Report anal sex with a man in the past 6 months
- Are able to complete survey instruments in English
- Live in the metropolitan area of a study site
- Are willing to provide at least 2 means of alternate contact
- Willing to not enroll in another HIV prevention trial
- HIV-negative (self-reported and lab confirmed)
- Own and willing to use a smart phone for the duration of the study
- Willing to download study app
- Willing to take a photo of a PrEP prescription label
- Behaviorally indicated for PrEP (per CDC guidance, Appendix 3) or if sexually active African American MSM
- PrEP naïve or < 3 months lifetime experience of PrEP use or stopped taking PrEP >6 months ago
- Willing to take PrEP including adherence to daily dosing
- Willing to use study-provided PrEP navigation services to obtain coverage for PrEP medication
- Able to work with study site to develop a plan to cover financial cost of PrEP if not covered through insurance or Gilead financial assistance
- Willing to use a home kit that will include self-administered collection of urine, rectal and pharyngeal swabs, and finger prick blood.

### **3.5.4 Exclusion Criteria**

- Not male sex at birth
- Reports having genital reassignment surgery
- HIV positive
- <18 or ≥ 50 years of age
- Currently enrolled in another HIV prevention trial
- Symptoms of acute HIV infection, or being evaluated for acute infection because of recent high risk exposure
- Currently taking PEP

---

 Based on WHO Guidelines of including populations at “substantial risk”

- Creatinine clearance <60 ml/min
- Contraindications to taking tenofovir disoproxil fumarate/emtricitabine (TDF/FTC) or tenofovir alafenamide/emtricitabine (TAF/FTC)
- History of hemophilia
- Unable to conduct finger prick at study site
- Health Insurance with Kaiser Permanente (unable to prescribe PrEP through the study)
- Investigator discretion to exclude anyone whose best interest is not to participate
- Evidence of fraudulent participation, such as duplicate IP address, multiple screening attempts, duplicate emails, etc

### **3.6 Recruitment Procedures**

For participants who meet eligibility criteria, we will ask for a first name, e-mail and phone number. For participants who do not screen eligible for the study, we will ask them if they want to provide their contact information for future studies for which they might be eligible. If they indicate interest in being contacted for future studies, we will request their contact information. These data will be stored in the secure, HIPAA-compliant servers of Alchemer.

Participants will have the opportunity to indicate that they prefer to be called by a study staff member and screened over the phone rather than completing the full study screener online. Participants will be asked to read an informed consent form and indicate consent prior to completing the online screening survey or to verbally indicate consent if being screened on the phone by a study staff.

Venue-based recruitment strategies may be used, in which staff attend known MSM venues or events to recruit for the study. Possible venues include bars, malls, clubs and events such as Gay Pride. During venue-based recruitment, study staff will obtain verbal consent and then administer screener questions using a handheld device. Flyers and similar forms of visual advertisement may also be posted in public and private venues such as clinics, bars, clubs, churches, stores, restaurants, colleges, coffee shops, public transit venues, etc.

#### **3.6.1 Primary recruitment methods**

Primary recruitment methods include targeted online recruitment strategies, venue-based recruitment, and flyers and visual advertisements reviewed by the Emory IRB. Links to the screener survey will be advertised through banners or electronic messages on social media platforms such as Facebook, Grindr, or Instagram.

#### **3.6.2 Secondary recruitment methods**

Other recruitment methods will be used if recruitment targets are not being met. These additional strategies may include recruiting individuals who have recently been prescribed PrEP but are not established in a follow-up routine. This recruitment strategy would require a change to the exclusion criteria to allow for individuals recently prescribed PrEP to enroll.

### **3.7 Participant Retention**

Once a participant enrolls in the study, study staff will seek to retain the participant throughout the follow-up period in order to minimize possible bias associated with loss-to-follow-up. Study staff will be responsible for developing and implementing standard operating procedures to target this goal. Retention efforts include an explanation of the study and procedural requirements during the informed consent process and re-emphasis throughout the study. Detailed contact information

will be collected at the study baseline visit, with active review and updating of this information throughout the study. Reminder mechanisms will be used through the application, including notifications and messaging. Staff will use electronic messages, telephone calls, or emails to serve as reminders prior to scheduled consultation visits. Missed visits will be immediately followed up, with rescheduling. Staff will attempt to reengage participants who have been unresponsive to scheduling attempts through the duration of the study.

### **3.8 Participant Withdrawal / Early Termination**

Participants may voluntarily withdraw from the study for any reason at any time. The study investigators also may withdraw participants from the study in order to protect participant or staff safety. Study staff will record the reasons for all withdrawals. Early study termination may occur for the following reasons:

- Participants who have a confirmed HIV-positive test.
- Participants also may be withdrawn if the study is terminated prior to its planned end date.
- Participants will be withdrawn from the study if the physician determines it is in the participant's best interest to discontinue participation in the study.

## **4. STUDY INTERVENTION**

The PrEP@Home System is a fully remote system for conducting PrEP care with the goal to serve as a virtual visit and to allow providers to renew PrEP prescriptions without an in-person visit. To allow this to happen, relevant study data will be provided to participants' PrEP-prescribing physicians. Data that would be collected as part of a standard quarterly PrEP follow-up visit, including all lab results and relevant participant behavioral survey results, will be shared with providers. Participants will need to sign a release form allowing us to share these test and behavioral survey results with their provider. The release form is uploaded to eIRB.

The PrEP@Home System includes the participant facing app, the clinician dashboard and the administrative system. Participants will be able to track their study schedule through an application and message study staff if needed. All participants will download the app in order to access the quarterly surveys and to be able to track the home testing kits. To manage study logistics, control participants will receive the same management system as the intervention.

### PrEP@Home System: Home Care Kit

Participants will receive the home care kit as a plain box via standard mail. The box includes self-collection components and specimen return shipping. Each specimen collection component has its own bag containing instructions and materials for the specimen collection along with biohazard sealable bags for specimen return. The instructions are optimized to facilitate quality specimen collection and ease of use. The shipping is tracked through the study management system.

Laboratory results and the survey results will be collated and uploaded to an electronic interface for study clinicians, the clinician dashboard. If laboratory and behavioral survey results do not show contraindications to PrEP continuation, the study clinician will have the choice to renew the prescription without a visit by the patient. If there is a laboratory or behavioral result that the study clinician wants to discuss with the participant, then a telemedicine appointment will be scheduled. For positive laboratory results, participants will be referred to care for follow-up.

## 5. TRIAL DESIGN

### 5.1 Study Arms

The Intervention group will be assigned to using the PrEP@Home system for 6 months and/or one year of follow-up PrEP care, including telemedicine visits if needed and home test kits. Participants in the Intervention group will have full access to the application. All PrEP consultations will be conducted via telemedicine unless there is a clinical need to be seen in-clinic. Participants will have the option of coming to the clinic for in-person linkage to care at the end of study, if clinics are open.

The Control group will be actively linked to a local PrEP provider for standard of care follow-up. Participants in the Control group will see portions of the study app pertinent to their participation in the study, including electronic surveys and kit tracking for the mail DBS card for TFV-DP. Partner institutions at each site are already implementing PrEP as standard of care in their community, and participants will be referred to these institutions for PrEP care. Each study site will have designated local clinics that have agreed to provide standard PrEP care to control arm patients.

### 5.2 Randomization

Upon completion of stage 3 eligibility assessment (successful initiation of PrEP as determined by photo of prescription label), participants will be randomized to either intervention (PrEP@Home, n=264) or control (standard of care, n=132). Participants will be randomized using an electronic data system, DFExplore. We will implement a stratified randomization scheme using categories of age (18-34, 35-49) and study site to decreases the likelihood of Type I error due to the expected association between covariates and study outcome. An uneven allocation ratio of 2:1 (Intervention : Control) will facilitate subgroup analyses and modeling for Aims 2 and 3 by allowing for larger intervention group size.

All randomization will be accomplished within the study data management platform; within each stratum, the data system will produce a sequential block randomization list. This list, not viewable by study PI's or the study statistician, will automatically populate the appropriate study arm assignment in the electronic data system at the time each new participant is randomized at any of the four study sites.

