## 9. STATISTICAL CONSIDERATIONS

### 9.1 Primary Outcome

Assessment of TFV-DP will be conducted at 6 and 12-month follow-ups. Differences in the proportion of participants with protective levels of TFV-DP between the intervention arm and the control arm will be tested using two-proportion z-tests with pooled variances, based on intent-to-treat assignment. The percentage of participants with protective levels of TFV-DP at months 6 and 12 will be compared using a Generalized Linear Mixed Model (GLMM) logistic regression model that accounts for within-participant correlation over time, of the form:  $\text{logit } \pi_{ij} = \beta_0 + \beta_1$

$\beta_2 \text{rm}_{ij} + \beta_3 (\text{time}_{ij}) + \beta_4 (\text{rm}_{ij} \times \text{time}_{ij})$ , where  $\pi_{ij}$  represents the outcome at time  $j$  on participant  $i$ ,  $\beta_0$  represents a random intercept for participant  $i$ , and fixed effect dummy variables are included for intervention arm, time, and the interaction between arm and time. The statistical model will be used to estimate the proportion of participants with protective levels of TFV-DP (plus 95% confidence intervals) by intervention assignment and time on study. The statistical test for interaction between arm and time will be the primary overall test to determine whether PrEP protection changed in significantly different ways during follow-up (at  $\alpha = 0.05$ ). If a significant time\*intervention interaction is detected, we will test differences between the model-based adherence estimates at each time point. If protective levels of PrEP rates are consistently different or similar (i.e., no interaction) then the main effect test for intervention assignment will be used to evaluate intervention efficacy.

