### **9.2.1 Adjusted analyses**

GLMM models will control for potential confounding for factors such as medication self-efficacy and motivation to take PrEP. (1) Adjusted analyses will be conducted to control for changes in PrEP eligibility over time for participants in each trial arm, per CDC guidelines, using an additional interaction term between eligibility and treatment arm. (2) Per protocol assessments will be conducted that account for potential changes in intervention as delivered; for instance, this would account for participants assigned to the intervention condition opting to instead receive standard of care PrEP from their local clinician.

A number of secondary analyses will be conducted using GLMM models. (3) Intervention impact on the secondary outcome of PrEP prescription persistence will be determined using analogous logistic regression models. (4) Secondary analysis will be conducted to model  $\log_{10}$  (TFV-DP levels), using a linear mixed model. Other specific and aggregate measures of safety include: renal function, HIV incidence, and incident bacterial STI across study arms.

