### **9.3 Exploratory analyses**

Exploratory analysis of intervention effectiveness across subgroups, and analysis of potential mediators of persistence in PrEP care across both study arms

Heterogeneity of the intervention effects across subgroups, including those stratified upon (city, age), and socioeconomic indicators, using unadjusted proportion tests and subgroups\*intervention arm interaction variables in GLMM models. We will examine expected mediators of primary and secondary study outcomes. Possible mediators are variables hypothesized to be on the causal pathway between the intervention and study outcomes (e.g. medication adherence self-efficacy, perceived benefits of PrEP, perceived ease of use of PrEP). For participants who seroconvert during the study, we will analyze levels of TFV-DP, PrEP persistence, and other clinically-relevant study data.

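### Age group and site define the randomisation strata but are left out of the z-test and the GLMM arm effect; including them would recover a little power at almost no cost

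*Combined protocol and SAP*

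**What the plan says.** Section 5.2 (Randomization): "We will implement a stratified randomization scheme using categories of age (18-34, 35-49) and study site". Lists are blocked within each stratum and allocation is 2:1 (264:132). The reason given is that these covariates are expected to be related to the outcome.

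Section 9.1 (Primary Outcome) gives two analyses of the proportion with protective TFV-DP levels:

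- The arm difference "will be tested using two-proportion z-tests with pooled variances, based on intent-to-treat assignment".
- A random-intercept logistic model in which "fixed effect dummy variables are included for intervention arm, time, and the interaction between arm and time". On its use: "The statistical test for interaction between arm and time will be the primary overall test". If there is no interaction, "then the main effect test for intervention assignment will be used to evaluate intervention efficacy".

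Neither contains age group or site. Elsewhere:

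- Section 9.2.1 (Adjusted analyses): "GLMM models will control for potential confounding for factors such as medication self-efficacy and motivation to take PrEP". The list is open, but it governs only the adjusted analyses.
- Section 9.3 uses city and age for exploratory subgroups, "including those stratified upon (city, age), and socioeconomic indicators".

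The number of site strata is also inconsistent. Section 5.2 ends with "at the time each new participant is randomized at any of the four study sites", Sections 3.1 and 3.4 name five metropolitan areas, and the key informant interviews in Section 9.5 imply three sites at one clinician each.

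**The concern.** Blocking within strata forces the arms to be nearly balanced on age group and site. If those factors predict the outcome, the arm difference varies less from trial to trial than under simple randomisation. An analysis that ignores the strata does not take credit for this: it leaves the between-stratum variation in its standard error. The test is then conservative and the confidence interval too wide.

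This bears on two results, the z-test and the GLMM arm effect. The second decides efficacy when no interaction is found. What is at stake is a little power and precision. The validity of the trial is not at stake.

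**Working it through.** **The plan's own power figure (Section 9.2).** Inputs: 396 enrolled, 2:1, 10% loss (about 119 control and 238 intervention), control 0.50, difference 0.158, two-sided alpha 0.05.

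- Pooled proportion = (119 × 0.50 + 238 × 0.658)/357 = 0.6053
- SE under the null = √[0.6053 × 0.3947 × (1/119 + 1/238)] = 0.0549
- SE under the alternative = √[0.25/119 + 0.658 × 0.342/238] = 0.0552
- Power = Φ[(0.158 − 1.96 × 0.0549)/0.0552] = Φ(0.914) = 82.0%

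This is consistent with the stated 80%.

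**Expected size of the unstratified z-test.** Let R² be the share of outcome variance explained by the strata. With balance inside every stratum, the true variance of the arm difference is (1 − R²) times what the z-test assumes, so

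size = 2 × [1 − Φ(1.96/√(1 − R²))].

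The documents give no R², so a range is assumed: five sites by two age groups (10 equal strata), equally spaced site effects with SD 0.3, 0.5 or 0.7 on the logit scale, an age difference of 0.4, 0.6 or 0.8, and a mean control proportion of 0.50. For the first setting the outermost strata lie at ±(0.3 × √2 + 0.2) = ±0.62 on the logit scale, that is 35% and 65%. Dividing the variance of the ten stratum proportions by 0.25 gives R² = 0.031, 0.076 and 0.132. The formula then gives sizes of 4.6%, 4.2% and 3.5%. Simulation with exactly 24:12 analysed per stratum gives 4.5%, 4.0% and 3.5%.

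**Simulation with 10% random loss** (264:132 randomised, mean 356 analysed, 200,000 trials per setting, common odds ratio giving a mean difference of 15.8 points). Loss breaks the balance a little, so the effect is smaller:

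| Control range across strata | Size, z-test / CMH | Power, z-test / CMH | z-test SE too large by |
|---|---|---|---|
| none | 5.1 / 5.1% | 82.0 / 81.8% | – |
| 35-65% | 4.6 / 5.0% | 82.3 / 82.9% | 1.5% |
| 27-73% | 4.3 / 5.0% | 82.7 / 84.5% | 3.5% |
| 20-80% | 3.8 / 5.1% | 83.3 / 86.5% | 6% |

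The Monte Carlo SE of a 5% size is 0.05 points. With four sites the power gains are 0.6, 1.8 and 3.1 points. At a milder spread of 42-58% (100,000 trials per setting), z-test size is 4.9-5.0% and the gain lies between nil and about 0.4 points.

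**Cause.** In a separate simulation with stratum rates of 16-84% (R² = 0.17), z-test size was 3.6% under stratified blocks and 5.2% under simple randomisation. The shortfall comes from ignoring the stratification.

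**GLMM arm effect** (random-intercept SD 2.0 assumed, months 6 and 12, Wald tests, 5,000 trials per setting), without / with age and site:

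| Control range | Size | Power | Interaction SE |
|---|---|---|---|
| 35-65% | 4.3 / 4.9% | 92.8 / 93.4% | 0.419 / 0.419 |
| 27-73% | 3.7 / 5.1% | 92.9 / 94.7% | 0.427 / 0.427 |
| 20-80% | 3.1 / 5.3% | 93.5 / 96.1% | 0.439 / 0.439 |

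The Monte Carlo SE of these sizes is 0.3-0.4 points. A second model (random-intercept SD 1.5, half with month 12, likelihood-ratio test, SE about 0.5 points) gives 4.9% without and 5.0% with the factors when there is no association, and 4.0% against 4.9% at R² = 0.09.

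The interaction is mainly a within-participant contrast, so omitting the strata hardly touches it. With half the participants at month 6 only, its SE changes by at most 1.4%.

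**The case against.** An unadjusted test after stratified randomisation is valid and errs on the safe side, and the planned power is met. This is a preference for efficiency. That stands, and it sets the low priority.

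The size of the effect is wholly assumed, and a weak association produces no visible shortfall. That also stands; the claim is conditional on the relation that Section 5.2 itself expects.

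The GLMM sizes depend on the model. With Wald tests and half the participants at month 6 only (3,000 trials per setting), sizes without / with the factors are 3.4 / 3.8%, 3.2 / 4.8% and 2.5 / 4.3%, so part of the shortfall is not due to the omission. At the smallest spread most of it is not. The z-test results are the firmer evidence.

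Aim 2.1 and Section 9.2.1 already promise adjusted analyses of the primary outcome. Those could include age and site, but they do not alter the tests in Section 9.1.

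Adding the factors makes the GLMM odds ratio conditional on them, and one Mantel-Haenszel risk difference is a weighted summary if stratum differences vary. Both are true. Standardised proportions by arm and time keep the result on an interpretable scale.

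The site count is largely editorial. The rule, age group by site, is clear whichever sites enrol, and the interview section is weak evidence on strata. The mismatch between four and five sites is real but secondary.

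**Conclusion.** The concern holds as an optional improvement. If age group and site predict the outcome as Section 5.2 expects, the z-test and the GLMM arm effect are mildly conservative. For the z-test, size is 4.6% to 3.8% and the power forgone is 0.6 to 3.2 points over control ranges from 35-65% to 20-80%. With no association, stratifying costs about 0.2 points of power. Type I error is not inflated, the aim stated in Section 5.2 is not defeated, and the interaction test is essentially unaffected. The figures rest on assumed stratum spreads, roughly equal strata and random 10% loss; the GLMM figures also rest on an assumed random-intercept SD.

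**What to change.** In Section 9.1:

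- Replace the z-test, at the same time point or points, with a CMH test stratified by age group and site. Report the Mantel-Haenszel risk difference with its 95% confidence interval. Pool the two age groups within a site only if a stratum has no participants in one arm. With assumed uneven strata, the smallest 8:4, the chance of any empty arm was 0.01%.
- Add age group and site as fixed main effects to the primary GLMM, and report standardised proportions by arm and time. The interaction test and its place in the plan stay as they are.

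In Section 5.2, reconcile the number of sites with Sections 3.1, 3.4 and 9.5 so that the strata are defined.

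The cost is two or three sentences and a corrected count, made before unblinded data are seen. Both factors are recorded at randomisation, so no further data or participants are needed.
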